6.11.2. Tumor Assessments

Tumor samples from archival tissues or biopsies will be collected. Subjects must have available tissue samples to enter the study. Alternatively, subjects must agree to have a biopsy taken prior to entering the study to provide adequate tissue. CCI [REDACTED]

6.11.2.1. Tissue Collection

Tumor tissue CCI [REDACTED] will be collected at the time of screening from a biopsy obtained preferably either at the time of or after the diagnosis of advanced disease has been made, and from a site not previously irradiated.

If a tumor biopsy was obtained from a target lesion during eligibility assessment, it is preferred that a new baseline scan be obtained.

CCI [REDACTED]

CCI

In Cohort 2 in Phase 1b, pretreatment and C3D1 biopsies are mandatory.

For additional details and instructions regarding tissue requirements, collection, storage and shipment, refer to the study Laboratory Manual.

6.11.2.2. Tumor Imaging

Investigator-assessed imaging will be done at defined time points. The initial tumor imaging to establish baseline disease will be performed \leq 28 days prior to first dose. Scans performed as part of routine clinical management are acceptable for use as screening scan if they are of diagnostic quality and \leq 28 days prior to first dose. On-study imaging as listed on [Table 6-18](#) will be performed as specified below and in [Appendix 2](#).

Table 6-18. Postbaseline Imaging Schedule

| Cohort | Postbaseline Imaging Schedule | Duration of Tumor Imaging Assessments |
|--|--|--|
| Phase 1a (all cohorts), Phase 1b Cohort 2 | Week 6, 12, 18, and 24 (\pm 7 days) from the first treatment dose; then every 12 weeks thereafter | Until PD is assessed by investigator, new line of therapy, or 1 year after first treatment dose, whichever occurs first |
| Phase 1b Cohort 1 | Week 6, 12, 18, and 24 (\pm 7 days) from the first treatment dose; then every 12 weeks thereafter | Until PD is assessed by investigator, new line of therapy, or 2 years after first treatment dose, whichever occurs first |

[figure not shown]
PD progressive disease

Note: For subjects who permanently discontinued all study drug(s) in the absence of PD (eg, experienced unexpected toxicity), CT or MRI imaging should continue to be performed until PD or initiation of a new anticancer therapy other than the study treatment, whichever occurs first (see Section [6.8.2](#)).

The timing of on-study treatment imaging should follow calendar days and should not be adjusted for delays in treatment administration or for visits. Additional imaging at the End-of-Treatment Visit and 30-Day Follow-up Visit is not required provided imaging assessments have been performed per schedule and last imaging must be performed within less than 30 days. Subjects that discontinue from the study for any reason other than PD will continue to have imaging/CT scans at the predefined schedule until documented PD or initiation of a new anticancer treatment.

The same imaging technique should be used in a subject throughout the study. In general, lesions detected at baseline should be followed using the same imaging methodology and preferably the same imaging equipment at subsequent tumor evaluation visits. The Investigator may perform scans in addition to a scheduled study scan for medical reasons or if PD is suspected.

CCI

7. ADVERSE EVENTS AND TOXICITY MANAGEMENT

7.1. Definitions of Adverse Events, Adverse Reactions, and Serious Adverse Events

7.1.1. Adverse Events

An AE is any untoward medical occurrence in a clinical study subject administered an investigational product, which does not necessarily have a causal relationship with the treatment. An AE can therefore be any unfavorable and/or unintended sign, symptom, or disease temporally associated with the use of an investigational product, whether or not considered related to the investigational product. Adverse events may also include pretreatment or posttreatment complications that occur as a result of protocol-specified procedures or special situations (Section 7.7). Preexisting events that increase in severity or change in nature during or as a consequence of participation in the clinical study will also be considered AEs. Adverse events should be reported as described in Section 7.3.

An AE does not include the following:

- Medical or surgical procedures such as surgery, endoscopy, tooth extraction, and transfusion. The condition that led to the procedure may be an AE and must be reported.
- Preexisting diseases, conditions, or laboratory abnormalities present or detected before the screening visit that do not worsen
- Situations where an untoward medical occurrence has not occurred (ie, hospitalization for elective surgery, social and/or convenience admissions)
- Overdose without clinical sequelae (Section 7.7.1)
- Any medical condition or clinically significant laboratory abnormality with an onset date before the informed consent form is signed and not related to a protocol-associated procedure is not an AE. It is considered to be preexisting and should be documented as medical history.

7.1.2. Serious Adverse Events

An SAE is defined as an event that, at any dose, results in the following:

- Death (**Note:** In the case of death, the primary cause of death or the event leading to death should be recorded and reported as an SAE. “Fatal” will be recorded as the outcome of this respective event; death will not be recorded as separate event. Only if no cause of death can be reported (eg, sudden death, unexplained death), might the death per se be reported as an SAE. Please refer to Section 7.1.2.3 for exceptions.)

- Life-threatening (**Note:** The term “life-threatening” in the definition of “serious” refers to an event in which the subject was at risk of death at the time of the event; it does not refer to an event that hypothetically might have caused death if it were more severe.)
- In-patient hospitalization or prolongation of existing hospitalization
- Persistent or significant disability/incapacity
- A congenital anomaly/birth defect
- A medically important event or reaction: such events may not be immediately life-threatening or result in death or hospitalization but may jeopardize the subject or may require intervention to prevent one of the other outcomes constituting SAEs. Medical and scientific judgment must be exercised to determine whether such an event is a reportable under expedited reporting rules. Examples of medically important events include intensive treatment in an emergency room or at home for allergic bronchospasm; blood dyscrasias or convulsions that do not result in hospitalization; and development of drug dependency or drug abuse.

7.1.2.1. Protocol-Specific Adverse Event Instructions

Given the intended mechanism of action, particular attention should be given to AEs that may result from enhanced T-cell activation, such as dermatitis, colitis, hepatitis, uveitis, or other immune-related reactions. When clinically indicated, ophthalmologic examinations should be considered for signs or symptoms of uveitis.

An irAE may be defined as an AE of unknown etiology, associated with drug exposure and is consistent with an immune phenomenon. Efforts should be made to rule out neoplastic, infectious, metabolic, toxin, or other etiologic causes prior to labeling an AE as immune related. Immunological, serological, and histological (biopsy) data should be used to support the diagnosis of an immune-related toxicity.

Complete, accurate, and consistent data on all AEs experienced for the duration of the reporting period (defined below) will be reported on an ongoing basis in the appropriate section of the eCRF. Any serious irAEs should be reported in accordance to Section 7.3.

It is important that each AE report include a description of the event, its duration (onset and resolution dates and times to be completed when it is important to assess time of AE onset relative to recorded treatment administration time), its severity, causal relationship with study treatment, any other potential causal factors, any treatment administered, or other action taken (including dose modification or discontinuation of the study drug), and outcome. In addition, serious cases should be identified, and the appropriate seriousness criteria documented.

Specific guidance can be found in the eCRF Completion and Monitoring Conventions.

7.1.2.2. Events of Clinical Interest

Events of clinical interest, regardless of seriousness, are to be reported within 24 hours to Gilead either by electronic media or paper. Gilead contact information can be found in the Investigator Study File Binder (or equivalent).

Events of clinical interest for this study include:

- An elevated AST or ALT lab value $\geq 3 \times$ ULN and an elevated total bilirubin lab value $\geq 2 \times$ ULN and, at the same time, an alkaline phosphatase lab value $< 2 \times$ ULN, as determined by way of protocol-specified laboratory testing or unscheduled laboratory testing.

Note: These criteria are based upon available regulatory guidance documents. The purpose of the criteria is to specify a threshold of abnormal hepatic tests that may require an additional evaluation for an underlying etiology.

7.1.2.3. Disease Progression

In order to maintain the integrity of the study, the following events that are assessed as unrelated to study drugs will not be considered SAEs:

- Disease progression of malignancy being studied
- Death due to disease progression of malignancy being studied

Disease progression and death due to disease progression of malignancy being studied should be reported as an SAE by the investigator only if it is assessed as related to study drug.

7.2. Assessment of Adverse Events and Serious Adverse Events

The Investigator or qualified subinvestigator is responsible for assessing AEs and SAEs for causality and severity, and for final review and confirmation of accuracy of event information and assessments.

7.2.1. Assessment of Causality for Study Drugs and Procedures

The investigator or qualified subinvestigator is responsible for assessing the relationship to study drug using clinical judgment and the following considerations:

- **No:** Evidence exists that the AE has an etiology other than the study drug. For SAEs, an alternative causality must be provided (ie, preexisting condition, underlying disease, intercurrent illness, or concomitant medication).
- **Yes:** There is reasonable possibility that the event may have been caused by the study drug.

It should be emphasized that ineffective treatment should not be considered as causally related in the context of AE reporting.

The relationship to study procedures (ie, invasive procedures such as venipuncture or biopsy) should be assessed using the following considerations:

- **No:** Evidence exists that the AE has an etiology other than the study procedure.
- **Yes:** The AE occurred as a result of protocol procedures (ie, venipuncture).

7.2.2. Assessment of Severity

Adverse events will be graded and recorded throughout the study and during the follow-up period according to NCI CTCAE v5.0. A general grading (severity/intensity) scale is provided at the beginning of the referenced document, and specific event Grades are also provided. If a particular AE severity/intensity is not specifically graded by the guidance document, the investigator is to revert to the general definitions of Grade 1 through Grade 5 and use his/her best medical judgment.

The 5 general Grades of AE severity are:

- Grade 1: Mild
- Grade 2: Moderate
- Grade 3: Severe
- Grade 4: Life-threatening or disabling
- Grade 5: Death related to AE

7.3. Investigator Requirements and Instructions for Reporting Adverse Events and Serious Adverse Events to Gilead

Requirements for collection prior to study drug initiation:

After informed consent, but prior to initiation of study medication, the following types of events must be reported on the applicable eCRFs: all SAEs and AEs related to protocol-mandated procedures.

7.3.1. Adverse Events

Following initiation of study medication, collect all AEs, regardless of cause or relationship, until the study's End-of-Treatment Safety Visit, 30 days after last administration of study drug and they must be reported on the eCRFs as instructed.

All AEs should be followed up until resolution or until the AE is stable, if possible. Gilead may request that certain AEs be followed beyond the protocol-defined follow-up period.

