The single dose plasma GS-1423 toxicokinetic data from a cynomolgus monkey non-GLP toxicology study were analyzed by noncompartmental analysis using the software WinNonlin. Pharmacokinetic (PK) parameters were allometrically scaled to obtain estimates of human volume of distribution at steady-state (Vd_{ss}), half-life, and accumulation ratio (AR). MABEL (EC₉₀ geometric mean of 3.28 μ g/mL) and volume of distribution (Vd) (7840 mL of standard 70 kg human body weight) were converted to a calculated human dose of 0.367 mg/kg. This dose was rounded down to a final GS-1423 starting dose of 0.3 mg/kg (Table 1-1). Further, 25.0 mg/kg is the HED based on a NOAEL of 75 mg/kg in cynomolgus monkey (ie, determined to be the most appropriate species for toxicological evaluation) and scaling using the mean 2.5 kg cynomolgus monkey body weight to a 70 kg human body weight. The difference between HED (at NOAEL) and MABEL-derived starting dose demonstrates that the starting dose provides an 83.3-fold margin-of-safety (Table 1-1). For this FIH study, the proposed GS-1423 dosing interval of Q2W is supported by the predicted 9.06-day half-life scaled to human and the calculated AR of 1.52. Thus, the proposed GS-1423 starting dose of 0.3 mg/kg Q2W takes into consideration of the acceptable risk-to-benefit profile outlined in this protocol and is expected to be pharmacologically active in humans as demonstrated by the EC₉₀ values in a human in vitro assay.

The highest dose of GS-1423 to be evaluated in subjects is 45 mg/kg Q2W, which is projected to provide exposure margins corresponding to \geq 4.7-fold of the rat NOAEL/STD10 and \geq 4.0-fold of the monkey NOAEL/HNSTD, assuming dose proportionality after 10 mg/kg.

Table 1-1. Calculation of GS-1423 Starting Dose from MABEL and Determination of Safety Margin

| Starting Dose MABEL | |
|---|---------------------------|
| Relevant assay | Cell proliferation |
| EC ₉₀ | 0.00328 mg/mL |
| Vd_{ss} for 70 kg human | 7840 mL |
| Calculated dose/70 kg human | 25.7 mg |
| Calculated MABEL dose | 0.367 mg/kg |
| MRSD-MABEL, rounded down | 0.3 mg/kg |
| HED NOAEL | |
| NOAEL dose group (cynomolgus monkey) | 75 mg/kg |
| HED based on NOAEL | 25 mg/kg |
| Safety margin (HED/starting dose MABEL) | 83.3 fold |

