5.5.4. Management of Potential Immune-Related Adverse Events

Immune-related AEs may be associated with immuno-oncology agents such as GS-1423 and will be categorized as AEs of interest in this study. An irAE is defined as an AE of unknown etiology, that is potentially associated with study drug exposure and is consistent with an immune-mediated phenomenon. Efforts should be made to rule out other etiologies prior to labeling an AE of clinical interest. Early recognition and management of irAEs may mitigate

severe toxicity. Investigators should also monitor subjects closely for potential irAEs, which may manifest after weeks of treatment, at the earliest. Such events may consist of persistent rash, diarrhea, colitis, autoimmune hepatitis, pneumonitis, encephalitis, arthritis, glomerulonephritis, cardiomyopathy, or uveitis and other inflammatory eye conditions.

Management algorithms have been developed to assist investigators in assessing and managing the following groups of irAEs: dermatological, gastrointestinal, pulmonary, hepatic, endocrine renal, and neurological, among others.

Adverse events (both non-serious and serious) associated with drug exposure and consistent with an immune phenomenon may represent an immunologic etiology. These irAEs may be predicted based on the nature of the study drugs, their mechanism of action, and reported experience with immunotherapies that have a similar mechanism of action. An irAE can occur any time from shortly after the first dose to several months after the last dose of treatment. Particular attention should be paid to AEs that may be suggestive of potential irAEs, as outlined below.

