6.8.2. Posttreatment Follow-up Phase Visits

All subjects who discontinue study treatment will have at least 1 posttreatment visit at 3 months (± 7 days) from last dose of study treatment. Subjects who discontinue all study treatment for any reason other than PD and/or start of new anticancer therapy will have imaging/CT scans at the predefined schedule until documented PD or initiation of a new anticancer treatment. Subjects who discontinue study drug treatment due to PD and/or start of a new anticancer therapy will not require imaging/CT scans and will move into Survival Follow-up thereafter.

Subjects who have discontinued all study drug treatment due to reasons other than PD and/or start of a new line of therapy should be followed with Posttreatment Follow-up Visits for up to 12 months from last study treatment dose or until PD and/or start of a new line of therapy. Every effort should be made to collect subject information on the start of new anticancer therapy, PD, and death.

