7.3.2. Serious Adverse Events

All SAEs, regardless of cause or relationship, that occurs after the subject first consents to participate in the study (ie, signing the informed consent) and throughout the duration of the study, up to 30-Day Follow-up Visit, must be reported on the applicable eCRFs and to Gilead PVE as instructed below in this section. This also includes any SAEs resulting from protocol-associated procedures performed after informed consent is signed.

Any SAEs and deaths that occur after the End-of-Treatment Visit but within 30 days of the last dose of study drug, regardless of causality, should also be reported.

Investigators are not obligated to actively seek SAEs after the protocol-defined follow-up period; however, if the investigator learns of any SAEs that occur after the protocol-defined follow-up period has concluded and the event is deemed relevant to the use of study drug, the investigator should promptly document and report the event to Gilead PVE.

- All AEs and SAEs will be recorded in the eCRF database within 24 hours.

Electronic Serious Adverse Event (eSAE) Reporting Process

- Site personnel record all SAE data in the eCRF database and from there transmit the SAE information to Gilead PVE within 24 hours of the investigator's knowledge of the event. Detailed instructions can be found in the eCRF completion guidelines.
- If for any reason it is not possible to record the SAE information electronically (ie, the eCRF database is not functioning), record the SAE on the paper SAE reporting form and submit within 24 hours to:

Gilead PVE: Fax: PPD
E-mail: PPD

- As soon as it is possible to do so, any SAE reported via paper must be transcribed into the eCRF database according to instructions in the eCRF completion guidelines.
- If an SAE has been reported via a paper form because the eCRF database has been locked, no further action is necessary.
- For fatal or life-threatening events, copies of hospital case reports, autopsy reports, and other documents are also to be submitted by e-mail or fax when requested and applicable. Transmission of such documents should occur without personal subject identification, maintaining the traceability of a document to the subject identifiers.

- Additional information may be requested to ensure the timely completion of accurate safety reports.

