8.7.2. Adverse Events

Clinical and laboratory AEs will be coded using the Medical Dictionary for Regulatory Activities (MedDRA). System organ class, high-level group term, high-level term, preferred term, and lower-level term will be attached to the clinical database.

Events will be summarized on the basis of the date of onset for the event. A treatment-emergent AE will be defined as any AE that begins on or after the date of first dose of study drug up to the last dose of study drug plus 30 days.

Summaries (number and percentage of subjects) of treatment-emergent AEs (by system organ class and preferred term) will be provided by treatment group.

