#### 7.1.5. Treatment-Emergent Adverse Events

##### 7.1.5.1. Definition of Treatment-Emergent Adverse Events

Treatment-emergent adverse events (TEAEs) are defined as 1 or both of the following:

- Any AEs with an onset date on or after the study drug start date and no later than 30 days after permanent discontinuation of study drug
- Any AEs leading to premature discontinuation of study drug.

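### Immune-related AEs that begin more than 30 days after the last dose are not actively collected and largely fall outside the treatment-emergent summaries, although the protocol expects onset up to several months later

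*Protocol*

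**What the plan says.** **Expected onset.** Protocol Section 5.5.4 classes irAEs as AEs of interest and states: "An irAE can occur any time from shortly after the first dose to several months after the last dose of treatment".

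**Collection.** Protocol Section 7.3.1 collects all AEs until "30 days after last administration of study drug and they must be reported on the eCRFs as instructed". Section 7.3.2 collects SAEs up to the 30-Day Follow-up Visit and, in any case, within 30 days of the last dose. Beyond that, "Investigators are not obligated to actively seek SAEs after the protocol-defined follow-up period"; a later SAE is reported only if the investigator learns of it and judges it relevant to study drug.

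**Counting.** Protocol Section 8.7.2 counts AEs as treatment-emergent "up to the last dose of study drug plus 30 days". SAP Section 7.1.5.1 uses onset "no later than 30 days after permanent discontinuation of study drug" and adds a second limb with no time limit: "Any AEs leading to premature discontinuation of study drug".

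**Visits.** Protocol Section 6.8.2 says: "All subjects who discontinue study treatment will have at least 1 posttreatment visit at 3 months". The schedules in Protocol Appendix 2 and SAP Appendix 1 mark a focused examination, vital signs, ECOG status, laboratory tests, and PK and ADA samples at that visit. The Review AEs row stops at the 30-Day Follow-up Visit.

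**The concern.** The protocol names a toxicity class as of interest, says when it can appear, and then closes the collection window before that period ends. Subjects are still seen at about 3 months, but the schedule does not ask about AEs there.

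Safety and tolerability is the primary objective of Part A, and Section 3.2.3.1 bases the RP2D on all available relevant clinical data. Events that are never asked about can only make late toxicity look smaller than it is. SAP Section 1 says the study ended after Part A and that Part B and Phase 1b will not start, so the practical stake is the completeness of the Part A safety report.

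**Working it through.** **1. The windows side by side (no model needed)**

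| Item | Source | Reaches to |
|---|---|---|
| Expected irAE onset | Protocol 5.5.4 | several months after last dose |
| Active AE collection | Protocol 7.3.1 | 30 days |
| Active SAE collection | Protocol 7.3.2 | 30-Day Visit / 30 days |
| Treatment-emergent AEs | Protocol 8.7.2; SAP 7.1.5.1 | 30 days (SAP: plus AEs leading to discontinuation) |
| Review AEs in the schedule | Protocol App. 2; SAP App. 1 | 30-Day Visit |
| Visit with examination, laboratory tests, PK and ADA | Protocol 6.8.2, App. 2 | 3 months |

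The mismatch follows from the text alone. The PK check below asks only whether 30 days can be defended as the end of relevant exposure.

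**2. Inputs.** Section 1.5 says that Q2W dosing is "supported by the predicted 9.06-day half-life scaled to human and the calculated AR of 1.52". It also gives Vdss 7840 mL for a 70 kg human and EC90 3.28 µg/mL. Doses are 0.3, 1, 3, 10, 20, 30 and 45 mg/kg Q2W.

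**3. Reproducing the protocol's figures.**
- AR = 1/(1 − 2^(−14/9.06)) = 1.521 (stated 1.52).
- MABEL dose = 0.00328 mg/mL × 7840 mL = 25.7 mg; 25.7/70 = 0.367 mg/kg (stated 25.7 and 0.367).

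Both agree, so a one-compartment, first-order model matches the protocol's own arithmetic.

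**4. Level 30 days after the last dose.** 30/9.06 = 3.31 half-lives, and 2^(−3.31) = 0.101.
- C0 = dose × 70 kg / 7.84 L
- Steady-state peak = 1.521 × C0
- Day-30 level = 0.101 × peak
- Days to EC90 = 9.06 × log2(peak/3.28)

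| mg/kg | C0 (µg/mL) | Day 30, steady state (µg/mL) | × EC90, steady state | × EC90, single dose | Days above EC90, steady state |
|---|---|---|---|---|---|
| 0.3 | 2.68 | 0.41 | 0.13 | 0.08 | 3 |
| 1 | 8.93 | 1.37 | 0.42 | 0.27 | 19 |
| 3 | 26.8 | 4.10 | 1.25 | 0.82 | 33 |
| 10 | 89.3 | 13.7 | 4.2 | 2.7 | 49 |
| 20 | 179 | 27.4 | 8.3 | 5.5 | 58 |
| 30 | 268 | 41.1 | 12.5 | 8.2 | 63 |
| 45 | 402 | 61.6 | 18.8 | 12.3 | 68 |

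At 10 to 45 mg/kg (4 of 7 levels), collection stops 49 − 30 = 19 to 68 − 30 = 38 days before predicted steady-state exposure drops below EC90. By day 90 the highest dose is at 0.19 × EC90.

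**5. Sensitivity.** With an assumed half-life of 7 to 12 days, the steady-state day-30 multiple is:
- 1.9 to 8.7 at 10 mg/kg
- 8.4 to 39 at 45 mg/kg
- 0.56 to 2.6 at 3 mg/kg
- at most 0.87 at 0.3 and 1 mg/kg

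At the 12-day end, 45 mg/kg would still be at 39.05 × 2^(−60/12) = 39.05/32 = 1.2 × EC90 on day 90. The 3-month visit covers the predicted period on the protocol's half-life, with little to spare at the top dose if elimination is slower.

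**The case against.** The 30-day cut-off is applied consistently across both documents, and several provisions reach beyond it:
- Grade > 1 events present at the 30-day visit are followed further (Protocol 6.8.1.2).
- The 3-month visit includes chemistry, hematology and endocrine tests, which bear on hepatic, renal and endocrine irAEs.
- New significant findings on focused examination are recorded as AEs (6.2.5.2), and 7.2.2 speaks of grading AEs during follow-up.
- Posttreatment safety data go into listings (8.7).
- The SRT evaluates DLT-type toxicities arising after day 28 if they exceed 33% at a dose level (3.2.3.4), and the SAP lists and summarizes late DLT-type events (7.1.6.3).

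These provisions are real, and they rule out one inference a reader might draw: that late irAEs are simply missed. Serious or DLT-type late events can still surface. None of the provisions requires anyone to ask about new non-serious irAEs after day 30. Section 6.2.5.2 is written for examinations before dosing, 7.2.2 concerns grading, 6.8.1.2 covers events already open, and listings and summaries show only what was collected.

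Three other stronger readings are not supported:
- **Drug well above EC90 at day 30 in all subjects.** This holds at 10 mg/kg and above, not at 0.3 or 1 mg/kg, and 3 mg/kg is borderline.
- **New anticancer therapy shortens the window below 30 days.** Section 5.5.7.1 moves the 30-day visit forward, but the AE and treatment-emergent windows run from the last dose or discontinuation, and 7.3.2 keeps SAE reporting to 30 days.
- **The gap drives the dose decision, most at high doses.** The MTD rests on 28-day DLTs. A dose-related loss of events is plausible from the exposure figures, but no data in the documents show it.

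**Conclusion.** The point holds in limited form. The protocol expects irAEs up to several months after the last dose, yet active collection and treatment-emergent counting stop at 30 days, apart from the SAP's limb for AEs leading to discontinuation. New late irAEs, especially non-serious ones, are not systematically collected and are left out of those summaries.

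Predicted steady-state exposure at 10 to 45 mg/kg is about 4 to 19 times EC90 at the cut-off and stays above EC90 until about days 49 to 68. This rests on one-compartment, dose-proportional kinetics, with half-life and volume scaled from monkey data. Section 1.5 itself assumes proportionality only after 10 mg/kg. The EC90 comes from an in vitro cell-proliferation assay and is not an irAE threshold, so falling below it does not exclude an event. The documents give no late-irAE rate, so the number of events lost cannot be computed. The mismatch of windows does not depend on the PK model.

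**What to change.** **Protocol, Appendix 2.** Add Review AEs, limited to irAEs and SAEs, at the 3-month posttreatment visit. Reconcile footnote a, which sends subjects with progression or new therapy to survival follow-up after the 30-day visit, with Sections 5.5.7.1 and 6.8.2, which give them the 3-month visit first. Every subject who stops treatment should have that visit.

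**Protocol, Sections 7.3.1 and 7.3.2.** Keep full AE and SAE collection to at least 30 days after the last dose, regardless of new therapy. Then continue active collection of irAEs and SAEs to the 3-month visit, recording the start date of any new anticancer therapy. Ending collection at new therapy without the 30-day floor would shorten the SAE reporting that 7.3.2 now requires.

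**SAP, Sections 7.1.5 and 7.1.6.** Keep the 30-day tables. Add one summary by dose level of irAEs and SAEs through the 3-month visit, flagging events that begin after new therapy.

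**Subjects already past follow-up.** The study ended after Part A, and a new table cannot recover events that were never collected. The SAP should summarize any post-30-day irAEs and SAEs that were captured, and the study report should state the limitation.

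**Cost.** One eCRF page at an existing visit and one table. Late events will be partly confounded by progression or new therapy, which the flag makes visible but does not remove.
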